10.3 Anti-drug antibody and neutralizing antibody (NAb) status

The ADA of rozanolixizumab will be measured using a three-tiered assay approach: screening assay, confirmatory assay and titration assay. Any sample confirmed positive for ADA will be assayed to determine whether there is neutralizing potential.

Evaluation of rozanolixizumab immunogenicity will be performed using data from all evaluable study participants in the SS, defined as all study participants who have an evaluable pretreatment (baseline) sample (negative or positive ADA sample status), and at least 1 evaluable post-Baseline value.

Study participants with an evaluable pretreatment (baseline) sample but without a single evaluable sample taken post-Baseline will be included in the reporting of pre-existing ADA but excluded from all other immunogenicity analyses.

10.3.1 Data consideration

ADA Sample Status

The ADA sample status will be determined for each pre-treatment (Baseline) and post-treatment (post-Baseline) visit where samples are taken for ADA analysis.

- Sample values that are either ‘negative screen’ or ‘positive screen’ and ‘negative immunodepletion’ will be defined as **ADA negative** if corresponding rozanolixizumab concentrations are equal or below the validated drug tolerance limit of the ADA assay (200µg/mL rozanolixizumab) allowing detection of 100ng/mL ADA
- Sample values that are either ‘negative screen’ or the combination of ‘positive screen’ and ‘negative immuno-depletion’, but with corresponding rozanolixizumab concentrations above the validated drug tolerance limit of the ADA assay, will be defined as ADA inconclusive
- Sample values that are ‘positive screen’ and ‘positive immunodepletion’ will be defined as **ADA positive**
- Samples that could not be tested for ADA status due to inadequate sample volume, mishandling, or errors in sample collection, processing, storage, etc, will be defined as **Missing**.

Neutralizing antibody (NAb) sample status (positive/negative/missing) will be determined for ADA positive samples. Samples that are NAb positive will be evaluated in a titration assay to quantify the NAb level and will be reported as titer.

Definition of ADA Baseline

Baseline for anti-drug antibody (ADA) for MG0007 should be the last measurement prior to receiving the very first rozanolixizumab (RLZ) infusion across all MG studies. Specifically, baseline for ADA is define as:

- MG0003 ADA baseline if participants randomized to RLZ groups in MG0003;
- MG0004 ADA baseline if participants randomized to placebo in MG0003 and enrolled in MG0004 before entering MG0007;
- MG0007 ADA baseline of first study cycle if participants randomized to placebo in MG0003 and enrolled straight into MG0007.

If the ADA sample status for the visit prior to the first dose of RLZ is missing, the last non missing sample will be used.

ADA/NAb Participant Status

The ADA participant status will be classified on study participant and group level as outlined below (Shankar et al. 2014; Rup et al, 2015). A description of how study participants will be categorized for the immunogenicity assessment is provided in [Table 10-1](#).

Individual study participants will be assessed for ADA participant status, composed of 6 categories: ADA negative, inconclusive, and ADA positive, whereby a positive participant’s

status is determined as originating from a treatment-induced, boosted, reduced or unaffected ADA response.

Study participants who are identified as being treatment-induced or treatment-boosted ADA-positive will be grouped as treatment-emergent (TE)-ADA positive participants. Study participants who are identified as being treatment-reduced or treatment-unaffected ADA-positive will be grouped as non-TE-ADA positive participants. Both TE-ADA positive and non-TE-ADA positive participants will be further classified as NAb negative or NAb positive.

The individual and combined ADA participant categories will be derived and summarized through each scheduled assessment visit (Day 1, Day 22, Day 43, Day 99 for Cycle 1, Day 1 and Day 43 for subsequent cycle, up to the last visit, and EOS visit), unless specified otherwise. Post-Baseline time points where no ADA sample was collected, will be ignored for the categorization.

Table 10-1: Terms and Definitions for ADA Status Evaluation in Study Participant

Classification	Classification Label	Definition
Individual participant categories		
1	Pre-ADA negative – treatment induced ADA negative (ADA-NEG)	Study participants who have an ADA negative sample at Baseline and at all sampling points post-Baseline up to the timepoint of interest.
2	Inconclusive	Study participants who have an ADA positive or negative Baseline sample and some post-Baseline samples are missing or inconclusive, while other post-Baseline samples are ADA negative up to the timepoint of interest.
3	Pre-ADA negative – treatment induced ADA positive (TI-POS)	Study participants who have an ADA negative sample at Baseline and have at least one ADA positive sample at any sampling point post-Baseline up to the timepoint of interest.
4	Pre-ADA positive – treatment boosted ADA positive (TB-POS)	Study participants who have an ADA positive sample at Baseline and at least one ADA positive sample at any sampling point post-Baseline up to the timepoint of interest, with increased titer values compared to Baseline (greater than a predefined fold difference increase from Baseline value which will be defined within the validation of the assay ie MSR of the assay).
5	Pre-ADA positive – treatment reduced ADA positive (TR-POS)	Study participants with an ADA positive sample at Baseline, and ADA negative samples at all sampling points post-Baseline up to the timepoint of interest.
6	Pre-ADA positive – treatment unaffected ADA positive (TU-POS)	Study participants with an ADA positive sample at Baseline and an ADA positive sample at any sampling point post-Baseline up to the timepoint of interest.

Table 10–1: Terms and Definitions for ADA Status Evaluation in Study Participant

		interest, with titer values of the same magnitude as Baseline (less than a predefined fold difference from the Baseline value which will be defined within the validation of the assay, ie MSR of the assay ¹).
Combined participant categories		
7	Treatment emergent ADA positive (TE-POS)	Includes study participants who are treatment induced ADA positive (category 3) or treatment boosted ADA positive (category 4).
8	Non-treatment emergent ADA positive (Non-TE-POS)	Includes study participants who are treatment reduced ADA positive (category 5) or treatment unaffected ADA positive (category 6).
9	Treatment emergent ADA positive – NAb positive (TE-POS, NAb-POS)	Includes study participants who are treatment emergent positive (category 7) and have at least one NAb positive sample.
10	Treatment emergent ADA positive – NAb negative (TE-POS, NAb-NEG)	Includes study participants who are treatment emergent positive (category 7) and have no NAb positive samples.
11	Non-treatment emergent ADA positive - NAb positive (Non-TE-POS, NAb-POS)	Includes study participants who are non-treatment emergent positive (category 8) and have at least one NAb positive sample.
12	Non-treatment emergent ADA positive - NAb negative (Non-TE-POS, NAb-NEG)	Includes study participants who are non-treatment emergent positive (category 8) and have no NAb positive samples.

Note: if a participant has no baseline ADA, then she/he can't be treated as "Inconclusive".

¹ The fold difference increase from baseline value, ie the minimum significant ratio (MSR=1.36) determined during assay validation, will be reported in the relevant tables, listings and figures. It reflects the fold difference in titer level that considered higher than the assay variation in titer determination.

10.3.2 ADA summaries

The following outputs will be presented on the SS.

Tables:

- Number and percentage of study participants with ADA (positive, negative, inconclusive, missing sample) and NAb (positive, negative, missing) sample status at the time of each visit will be summarized by study cycle, actual dose level received within study cycle and RLZ total. Denominator is the number of study participants having a non-missing result at that visit.
- Number and percentage of study participants in each of the individual and combined ADA participant status categories presented in [Table 10–1](#) will be summarized by entire study (for Baseline up to EOS and Baseline up to Last Visit), study cycle (for Baseline up to Day 1 and Baseline up to Day 43), actual dose level received within study cycle and RLZ total. The

table will be repeated by prior treatment immediately before entering MG0007 (RLZ or placebo) at Last Visit only.

- Total prevalence of pre-existing ADA and NAb, defined as number and percentage of participants having an ADA/NAb positive sample status at baseline, with the denominator being the total number of study participants having an evaluable sample result at baseline. Missing samples will not be included in the denominator. The table will be repeated by prior treatment immediately before entering MG0007 (RLZ or placebo).
- The first occurrence of treatment-emergent ADA positivity: cumulative number and percentage of TE-ADA positive participants (category 7) who are ADA positive for the first time at each visit by treatment group and RLZ total. The table will be repeated by prior treatment immediately before entering MG0007 (RLZ or placebo).
- Summary table of mean maximum percentage CFB in total IgG up to Day 43 and mean CFB in MG-ADL at Day 43, summarized by ADA participant categories 1, 2, 9, 10, 11 and 12 by treatment group and RLZ total and by study cycle (for Baseline up to Day 43).
- Overall summary table of TEAEs at Last Visit summarized by ADA participant categories 1, 2, 7 and 8 for the corresponding time period of interest by the most recent treatment group and RLZ total.
- Summary table of incidence of TEAE at Last Visit by ADA participant category 1, 2, 7 and 8 for the corresponding time period of interest by the most recent treatment group and RLZ total.
- Summary table of AEOF hypersensitivity reactions, anaphylactic reactions and injection site reactions (defined as AEOF in [Section 13.7](#)) at Last Visit by ADA participant category 1, 2, 7 and 8 for Baseline up to Last Visit by the most recent treatment group and RLZ total.

Figures:

- Individual time course plots for ADA positive study participants with at least one ADA positive sample, representing ADA and NAb titers (on log-scale), percentage CFB for total IgG and MG-specific autoantibodies, and CFB for MG-ADL total score. The sub-title of the graph will include the study participant number, bodyweight category, treatment group (including prior treatment group in MG0003), study cycle, and individual ADA participant category (3, 4, 5, 6) up to last assessment of each cycle. The dosing will be represented in the x-axis with bars/arrows at the time of dose.
- A box-and-whisker plot of maximum postdose ADA titer (on log-scale) through Day 43 of each cycle versus ADA participant category for categories 9, 10, 11 and 12 (determined for the corresponding time period of interest) by study cycle. The same plot will be repeated for NAb titer for ADA participant categories 9 and 11.
- Time course plot of mean CFB in MG-ADL total score, summarized by ADA participant category 1, 2, 9, 10, 11 and 12. Categories will be determined for the time period from baseline up to Day 43 for each cycle. Separate plots for each treatment group and by study cycle.

- Spaghetti plots of individual time course of percentage CFB for total IgG, for each of the ADA participant categories 1, 2, 9, and 10 and time period of interest (Baseline up to Last Visit) whereby the ADA participant categories are multipaneled. Separate plots for each treatment group. Individual samples that tested positive for ADA will be visualized using a symbol and/or color. Dosing time points should be indicated below the x-axis.
- Scatter dot plot of individual CFB in MG-ADL total score categorized by ADA titer tertile (including category ADA not present) for each scheduled assessment (Day 22, Day 43, Day 99 for Cycle 1, Day 1 and Day 43 for subsequent cycle). The same plot will be repeated for NAb titer.
- Scatter dot plot of individual percentage CFB for total IgG categorized by ADA titer tertile (including category ADA not present) for each scheduled assessment (Day 22, Day 43, Day 99 for Cycle 1, Day 1 and Day 43 for subsequent cycle). The same plot will be repeated for NAb titer.

Listings:

- By-subject listing by study cycle, treatment group, and timepoint, of ADA and NAb sample status, ADA titer, NAb titer, rozanolixizumab plasma concentration, percentage CFB for total IgG and IgG subclasses, CFB for MG-specific autoantibodies, CFB for MG-ADL total score, QMG and MG-C. In addition, the time since administration of IMP will be reported (in days).
- By-subject listing by study cycle, treatment group, and timepoint, of ADA and NAb sample status, ADA titer, NAb titer, and AEs.

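### Safety events are tabulated by ADA category cumulated to Last Visit, without regard to whether the event came before or after the first treatment-emergent positive sample

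*SAP*

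**What the plan says.** SAP 10.3.2 plans three safety tables by ADA participant category:

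- "Overall summary table of TEAEs at Last Visit summarized by ADA participant categories 1, 2, 7 and 8".
- "Summary table of incidence of TEAE at Last Visit by ADA participant category 1, 2, 7 and 8".
- "Summary table of AEOF hypersensitivity reactions, anaphylactic reactions and injection site reactions", which is presented "at Last Visit by ADA participant category 1, 2, 7 and 8 for Baseline up to Last Visit by the most recent treatment group".

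The categories come from SAP Table 10-1. Category 7 (treatment-emergent positive) combines treatment-induced and treatment-boosted positives. To be treatment-induced, a Baseline-negative participant need only "have at least one ADA positive sample at any sampling point post-Baseline up to the timepoint of interest". Category 1 is the opposite extreme: "Study participants who have an ADA negative sample at Baseline and at all sampling points post-Baseline up to the timepoint of interest". Category 8 is Baseline-positive without boosting, and category 2 is inconclusive.

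ADA is sampled at "Day 1, Day 22, Day 43, Day 99 for Cycle 1, Day 1 and Day 43 for subsequent cycle", plus the last and end-of-study visits. ADA Baseline "should be the last measurement prior to receiving the very first rozanolixizumab (RLZ) infusion across all MG studies".

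SAP 8.2.1 shows adverse events as participants, percentage and number of events, with a TEAE window that runs to 56 days after the last dose of each cycle. Participants stay until approval or a managed access program (SAP 2.3.1), but for 14 months in Denmark and the UK (Protocol 10.8). Planned time-in-study categories run from under 3 months to 36 months or more (SAP 8.1).

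**The concern.** A reaction in Cycle 1 in someone whose first positive sample comes in Cycle 5 is tabulated as a reaction in an ADA-positive participant. The table cannot show that the event came first.

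Each further cycle adds ADA samples, which make it harder to remain in category 1. It also adds another TEAE window, which makes an event more likely. Both therefore rise with time in study, and a crude percentage corrects for neither. The only per-participant-year rate in the SAP is the number of cycles (SAP 8.1).

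The plan aligns other things more carefully. In these same tables dose is the most recent level before onset (SAP 3.6), and MG-ADL and IgG by ADA category are limited to Baseline up to Day 43 of each cycle. Only ADA status in the safety tables is left unaligned.

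Hypersensitivity is a named safety concern (Protocol 2.3), and Protocol 9.4.2.4 foresees exploring associations between ADA and safety. Readers will compare these columns even without a test.

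**Working it through.** The documents give no ADA or event rate for these tables, so there is no planned figure to reproduce. The check asks what the planned layout shows when ADA and events are truly unrelated.

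**Model 1, calendar time.** All inputs are assumptions:

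- follow-up uniform from 0.25 to 3 years;
- conversion rate a = 0.15 to 0.6 per year;
- first-event rate e = 0.1 to 0.5 per year for uncommon reactions and 3 per year for any TEAE;
- conversion and events independent.

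Let M(k) = [exp(−0.25k) − exp(−3k)] / (2.75k), the mean probability of no occurrence at rate k. Then:

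- event proportion in ADA-negatives = 1 − M(a+e)/M(a);
- event proportion in ADA-positives = 1 − [M(e) − M(a+e)] / [1 − M(a)].

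Example with a = 0.3 and e = 0.2: M(0.3) = 0.632, M(0.2) = 0.732, M(0.5) = 0.480.

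- Negatives: 1 − 0.480/0.632 = 24.1%.
- Positives: 1 − 0.252/0.368 = 31.5%.
- Ratio 1.31, where the truth is 1.
- Share of positives' first events that precede conversion: [e/(a+e)·(1 − M(a+e)) − M(a) + M(a+e)] divided by the joint probability of event and positivity = 0.056/0.116 = 48%.

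Two variations:

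- *A share p is already positive at entry.* Multiply M(a) and M(a+e) by (1 − p). In the example with p = 0.3, the ratio is 29.0%/24.1% = 1.20.
- *Every such event ends dosing and sampling.* P(positive) = a/(a+e)·(1 − M(a+e)) = 0.312. P(event before conversion) = e/(a+e)·(1 − M(a+e)) = 0.208. P(event) = 1 − M(e) = 0.268. The ratio is (0.060/0.312)/(0.208/0.688) = 0.64.

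| Scenario, no true association | Ratio positive/negative |
|---|---|
| Uncommon reaction, all negative at entry | 1.21–1.46 |
| Same, 30% already positive at entry | 1.10–1.38 |
| Any TEAE at 3 per year, all negative at entry | 1.05–1.08 |
| Uncommon reaction, every event ends dosing and sampling | 0.55–0.74 |

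In the first row, 41–56% of first events in ADA-positive participants precede conversion. In the second row it is 18–29%.

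**Model 2, per cycle.** TEAE windows and ADA samples accrue by cycle. A 6-week treatment plus 16-week observation cycle is 154 days, and 1080/154 = 7.0, so cycles were taken as uniform on 1 to 7, or 1 to 12 for shorter gaps (assumed). With C cycles, P(positive) = 1 − (1−a)^C and P(event) = 1 − (1−e)^C, averaged over C. Conversion was 5–20% per cycle.

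- a = 10%, e = 5%, 1 to 7 cycles: 21.7% against 16.4%, ratio 1.33.
- e = 2–10%: 1.25–1.48 with up to 7 cycles, and up to 1.79 with up to 12 cycles and 20% conversion per cycle.
- Any TEAE at 50% per cycle: 1.08–1.17.
- 20% already positive at entry: 1.14–1.69.
- Half of events end treatment: 0.79–1.01. All events end treatment: 0.41–0.68.
- Everyone followed for exactly 4 cycles: 18.5% in both groups, ratio 1.00. Unequal follow-up is what creates the ratio in this model.

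**After the change.** With status taken at onset and time at risk as denominator, the event rate is the same in both states by construction. Simulation of the no-stopping cases returned 0.99–1.01 for model 1 and 0.99–1.02 for model 2.

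**The case against.** Several points on the other side stand.

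- **Size for all TEAEs.** A reader might apply the 1.2 to 1.5 range to all three tables. It does not fit the two general TEAE tables: when nearly everyone has an event, little room is left for a difference.
- **Prior exposure.** ADA Baseline precedes the first rozanolixizumab dose in any MG study. Participants who converted in MG0003 or MG0004 have no MG0007 event before positivity, which pulls both the ratio and the misordered share down.
- **Direction.** A reader might infer that the tables must overstate risk in ADA-positive participants. The documents do not support that. Protocol 7.1.4 (criterion 8) requires permanent discontinuation after certain severe or serious reactions, which can cut later ADA sampling and push the ratio below 1.
- **Follow-up range.** The SAP 8.1 bins are display categories, and the last is adjusted to the data. They do not establish a uniform spread up to 3 years.
- **Purpose.** No testing is planned (SAP 4.1, 4.6), and Protocol 9.4.2.4 makes the associations exploratory.
- **Partial cover.** SAP 10.3.2 plans a by-subject listing of ADA status, titer and AEs by timepoint, and a table of first treatment-emergent positivity. With about 200 participants, the order of rare events can be read case by case.

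These points limit size and weight but do not remove the defect. The listing is not a tabulation, the first-positivity table is not linked to events, and SAP 8.2.3 names the reaction-by-ADA summary without adding timing. The reference to a corresponding period of interest in the two TEAE tables is loose, but with Last Visit as the timepoint it reads naturally as Baseline to Last Visit, which the reaction table states outright.

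**Conclusion.** The concern holds in a limited form. Cumulative ADA category, crude percentages and unequal follow-up together give a comparison that cannot separate events before positivity from events after it, and that time in study alone can distort.

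Under no true association the ratio is about 1.1 to 1.5 for uncommon reactions, with the lower end applying when some participants are already positive at entry. It goes higher only when fast conversion is combined with many cycles. For any TEAE it is about 1.0 to 1.1, or a little more in the per-cycle model. It falls below 1 if reactions end dosing and sampling. These sizes rest on assumed rates and an assumed spread of follow-up; the mechanism rests on the SAP's own definitions.

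A reader might also infer that the safety conclusions of the study are at risk. They are not: the tables are descriptive, and the primary endpoint (occurrence of TEAEs and TEAEs leading to IMP withdrawal) does not use ADA category. This is a cheap improvement to how immunogenicity and safety are reported.

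**What to change.** 1. Keep the three Last-Visit tables. Add a footnote that the category is cumulative to Last Visit and not aligned to event onset.
2. At least for the hypersensitivity, anaphylactic and injection-site table, add a table by ADA status at onset: before versus on or after the first treatment-emergent positive sample, whether treatment-induced or boosted. For participants already treatment-emergent positive at entry, start the positive state at MG0007 Day 1. Give participants, events and events per participant-year in each state.
3. Show category 8 and category 2 as separate rows. A single split at any positive sample would lose the treatment-emergent distinction. Negatives with missing or inconclusive samples also fall into category 2, and more samples give more chances of that.
4. Flag events between the last negative and the first positive sample as of uncertain order. After Cycle 1, in-cycle samples are at Day 1 and Day 43 only, so the first positive date is not the conversion date.

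No new data are needed, since ADA samples and AEs already come together in the planned by-subject listing. The cost is some extra programming and small cell counts, which should be presented as such.

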10.4 Immunology

All analyses described in this section will be based on the SS.

10.4.1

variables will be listed by treatment group, visit and time point including changes from Baseline for each cycle.

10.4.2 Serum cytokines

Cytokines results will be listed by treatment group, visit and time point for each cycle.

10.4.3

[REDACTED]

11 OTHER ANALYSES

The tables and figures described in this section will use SS. All listings will be presented using FAS unless otherwise noted.

11.1 Dose change in use of concomitant medications over time

The following summaries will be produced by study cycle using SS in all participants:

- The number and percentage of participants with dose change (dose increase, dose decrease) in use of steroids (ATC3 code: [REDACTED]), immunosuppressants (ATC3 code: [REDACTED]) or AChE Inhibitor (ATC3 code: [REDACTED]) during the study;
- Average daily dose (ADD) of above medications by preferred term (PT) at Baseline and last study visit (in general EOS visit);

Note: ADD of above medications will be calculated for each PT according to the dose and dose frequency on Prior and Concomitant Medications CRF (eg ADD of a participant taking steroid 20 mg QOD is 10 mg). Baseline ADD will follow the same Baseline definition in [Section 3.3](#), which will be calculated using the steroid dose taken prior to first IMP in MG0007. ADD at last study visit is calculated using the dose taken at last available visit.

- The change from Baseline of average daily dose (ADD) at last study visit, calculated as
ADD at last study visit – Baseline ADD;
- A listing will be provided for study participants in SS with dose change of steroids, including MG-ADL total score at Baseline and last study visit (EOS visit), last MG-ADL score prior to first steroid dose change, maintenance dose of RLZ, Baseline steroid ADD and steroid ADD at last study visit.

Note: Maintenance dose of RLZ is the most recent dose of RLZ when last steroid dose is given.

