6.5 Concomitant medication(s)/treatment(s)

6.5.1 Permitted concomitant treatments (medications and therapies)

Concomitant medications listed in [Table 6-3](#) are permitted during the study for the treatment of gMG, and dose adjustments are allowed between treatment cycles. With the exception of corticosteroids and AChE inhibitors, the dose of permitted concomitant medications should be maintained during each 6-week treatment cycle and every effort should be made to maintain a stable dose during the first 8 weeks of each Observation Period. Any violation of the permitted treatment criteria would lead to prohibited treatment and should be discussed with the Investigator, Sponsor, and Medical Monitor.

If a study participant receives a COVID-19 vaccine, the product name and date of administration(s) should be captured in the eCRF as a concomitant medication.

Table 6-3: Permitted concomitant treatments

Permitted Medications	Dose
Oral corticosteroids (eg, prednisolone)	No specific requirements
Methotrexate	≤30mg/week
Mycophenolate mofetil	≤3g/day
Cyclosporine ^a	≤5mg/kg/day for unmodified ≤4mg/kg/day for modified (microemulsion)
Azathioprine	≤3mg/kg/day
Cholinesterase inhibitors	≤600mg pyridostigmine/day
Tacrolimus ^b	≤5mg/day

^a Doses higher than listed are permissible if trough level is ≤300ng/mL.

^b If the total daily weight-based dose is >5mg, then a plasma trough level should be checked to ensure study participant is not above the recommended therapeutic range.

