6.5.4 Rescue medication

The study site will supply rescue therapy that will be obtained locally. Rescue therapy will be given as per standard of care and at the discretion of the Investigator. Study participants who continue to experience moderate to severe symptoms despite treatment with rozanolixizumab may be treated with the following as rescue therapy:

- IVIg
- SC Ig
- PEX, or plasmapheresis
- iv corticosteroids at a higher dose than previous oral dose

Participants who are treated with rescue therapy during the Treatment Period are not eligible to receive any further treatment with rozanolixizumab. Study participants must complete the first 8 weeks of the Observation Period after the last dose of rozanolixizumab prior to completing the EOS visit assessments, and subsequently will be withdrawn from the study (Section 4.4).

Those patients who received rescue therapy during the observation or no treatment with rozanolixizumab periods may continue in the study at the Investigator's discretion and after discussion with Medical Monitor and/or UCB Study Physician. The following cycle of rozanolixizumab should in general not start earlier than 4 weeks following the last dose of IVIg, SC Ig, or iv corticosteroids or the last PEX session, unless there is a medical reason, and an earlier treatment initiation is being considered █ for the study participant as agreed upon with the Medical Monitor and/or UCB Study physician.

The date and time of rescue medication administration as well as the name and dosage regimen of the rescue medication must be recorded.

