8.1.4 Patient-reported outcomes

Patient-reported outcomes must be completed as per time points mentioned in the Schedule of Activities (Section 1.3). The PROs should be completed prior to any intrusive procedures in a quiet place.

The PROs should be completed in the following order: MG-ADL, MG Symptoms PRO, EQ-5D-5L, and MG-QOL15r. The PROs should only be checked for completeness. On dosing days, the

PROs will be completed prior to dosing. Study participants should not take pyridostigmine (or other AChE inhibitor medication) from midnight before the days when efficacy assessments are performed, when medically safe to do so to standardize testing.

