9.1 MG-ADL score

The complete list of MG-ADL items and scores are provided in [Table 13-3](#). The total score will be calculated according to the rules set down in [Section 13.3](#).

The MG-ADL total score and change from Baseline will be summarized by study cycle, actual dose level received within study cycle, and RLZ total using descriptive statistics.

The above MG-ADL summaries will be repeated for COVID-19 free study participants, where COVID-19 free participants for this SAP exclude:

- Study participants who discontinue treatment due to suspected/confirmed COVID-19 infection (“Confirmed COVID-19” or “Suspected COVID-19” as the relationship to COVID-19 in the COVID-19 Impact eCRF);
- Study participants who discontinue treatment due to non-infection related COVID-19 issues (“General circumstances around COVID-19 without infection” or “other” as the relationship to COVID-19 in the COVID-19 Impact eCRF);
- Study participants have visits affected in treatment period (eg visit performed by video call) due to COVID-19 pandemic.

The subgroup summaries will be performed as specified in [Section 4.9.1](#). Additional summary by fixed dose and weight subgroups will also be conducted as specified in [Section 4.9.2](#).

The MG-ADL total score (excluding ocular items) with associated change from Baseline will be summarized by study cycle, actual dose level received within study cycle, and RLZ total using descriptive statistics.

The mean change from Baseline in MG-ADL over time will be plotted by study cycle and treatment group.

A boxplot of change from Baseline in MG-ADL at Day 43 will be generated by study cycle and administered dose as specified in [Section 4.9.2](#).

By-participant listings of MG-ADL values will be provided. In addition, listing of MG-ADL by study cycle and dose will also be provided.

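### The by-cycle concomitant-dose tables in SAP 11.1 do not measure dose change within a cycle, so an oral corticosteroid increase before Day 43 that is later tapered can show as zero

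*SAP*

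**What the plan says.** Protocol 6.5.1 sets the rule on background treatment: "With the exception of corticosteroids and AChE inhibitors, the dose of permitted concomitant medications should be maintained during each 6-week treatment cycle". In Table 6-3 the dose entry for oral corticosteroids is "No specific requirements"; for cholinesterase inhibitors it is "≤600mg pyridostigmine/day". The rescue list in Protocol 6.5.4 includes corticosteroids only as "iv corticosteroids at a higher dose than previous oral dose". For patient-reported outcomes, Protocol 8.1.4 adds, subject to medical safety: "Study participants should not take pyridostigmine (or other AChE inhibitor medication) from midnight before the days when efficacy assessments are performed". Protocol 8.1.2 and 8.1.3 say much the same for QMG and MG-C.

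SAP 11.1 opens with "The following summaries will be produced by study cycle using SS in all participants". It then plans:

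- the number and percentage of participants with a dose increase or decrease in steroids, immunosuppressants or AChE inhibitors, worded as covering the whole study;
- ADD at Baseline and at the last study visit (in general EOS), and the change between them;
- a listing of participants whose steroid dose changed.

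The note on ADD refers to the Baseline definition in SAP 3.3 and then describes Baseline ADD as one "which will be calculated using the steroid dose taken prior to first IMP in MG0007".

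The efficacy tables work cycle by cycle. SAP 9.1 states: "The MG-ADL total score and change from Baseline will be summarized by study cycle, actual dose level received within study cycle". Protocol 9.4.1 names the Day 1 to Day 43 MG-ADL change, in each of the first three cycles and against that cycle's own Baseline, as the main efficacy endpoint.

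**The concern.** An oral corticosteroid increase early in a cycle is permitted and is not rescue. It is not one of the intercurrent events in SAP 3.9, and it enters that cycle's Day 43 result unmarked. The study has no placebo arm, and SAP 4.7 plans no sensitivity analysis of efficacy. A reader of a Day 43 table will therefore want to know how often background therapy rose over the same six weeks. SAP 11.1 is the only section that summarises dose change, and its heading suggests that it answers this by cycle. Its start and end points do not.

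Two things are at stake. The first is a specification that a programmer cannot turn into a meaningful by-cycle table. The second is the objective of assessing the need for gMG medications, including changes in dose: it would be served by a study-long difference only, with no view of what happened during treatment.

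**Working it through.** The plan gives no figure for the frequency or size of dose changes, so there is none to reproduce. The one piece of arithmetic in SAP 11.1, its ADD example, is correct: 20 mg every other day = 20/2 = 10 mg/day.

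**Step 1. Which Baseline applies?** The SAP 11.1 heading says by study cycle. SAP 3.3 defines Baseline for by-cycle analyses as the last value up to the first IMP of that cycle, and for entire-study analyses as the last value up to the first IMP in MG0007. The note cites 3.3 and then spells out the second. Both readings can be argued from the text.

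**Step 2. Does the choice settle the matter?** The rule is: ADD change = ADD at last study visit − Baseline ADD. I applied it to two assumed steroid paths (mg/day; illustrative, not document data) under both readings.

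*Path 1:* 10 before the study and at Day 1 of each cycle; 20 at Day 43 of each cycle; tapered between cycles; 10 at the last visit.

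*Path 2:* 20 before the study and through cycle 1, 15 through cycle 2, 10 through cycle 3, 5 at the last visit; changes occur only between cycles or after the last one.

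| Quantity | Path 1, cycles 1, 2, 3 | Path 2, cycles 1, 2, 3 |
|---|---|---|
| True Day 1 to Day 43 change | 20−10 = +10, +10, +10 | 0, 0, 0 |
| SAP rule, study-level Baseline | 10−10 = 0, 0, 0 | 5−20 = −15, −15, −15 |
| SAP rule, per-cycle Baseline | 10−10 = 0, 0, 0 | 5−20 = −15; 5−15 = −10; 5−10 = −5 |

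Under the study-level reading every cycle carries the same number. Under the per-cycle reading the numbers differ, but each still runs through all later cycles to the last visit. Neither recovers the within-cycle change: Path 1 hides three increases, and Path 2 shows reductions in cycles where nothing changed between Day 1 and Day 43.

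**Step 3. Do the counts fill the gap?** Increases and decreases are separate categories, so they do not offset each other. But the bullet is worded for the study as a whole. Even if it is read by cycle, SAP 3.2.2 makes a cycle the Treatment Period, the 16-week Observation Period and the non-treatment period. Up to Day 155, Days 1 to 43 make up 43/155 ≈ 28% of the cycle, and less if a non-treatment period follows. An increase on Day 20 and one on Day 120 count alike, and no size is reported.

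**Step 4. Does anything else fill it?** The SAP 11.1 listing covers steroids only. It shows MG-ADL at Baseline, at the last visit and before the first steroid change, but not at Day 43 of each cycle. SAP 6.4.2 assigns medication use to periods, not dose change. No subgroup in SAP 4.9.1 uses background-dose change. No planned table sets dose change between Day 1 and Day 43 beside Day 43 scores.

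**The case against.** The strongest reply is that the note in SAP 11.1 cites Section 3.3 and sits under a by-cycle heading, so the per-cycle Baseline is what was meant and one clarifying line would do. This stands for the start point: the text is ambiguous and need not be read as study-level. It does not rescue the end point, which is the last study visit on either reading.

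A reader might infer that the plan's only concomitant-dose analysis is the study-long one. The documents do not support that. The counts in the same section are a second analysis and would register an increase even if it were later reversed. The medication listings in SAP 6.4, with reported dates, also allow case-by-case review.

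A reader might also infer that both drug classes can be raised without restraint. That fits oral corticosteroids. AChE inhibitors have the pyridostigmine ceiling in Table 6-3 and are withheld from midnight before assessments when medically safe, which reduces their scope to influence the scores.

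It is also fair to say that efficacy here is secondary and descriptive, that MG0003 supplies placebo-controlled data for a single cycle, and that the endpoints listed for the medication-need objective are rescue use, time to rescue and healthcare utilization. A study-long dose change is a sensible summary of long-term need. These points limit the weight of the concern. They do not make the by-cycle tables informative.

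**Conclusion.** The point holds as a defect in specification. As written, the by-cycle ADD change does not measure change within a cycle, and the increase/decrease counts lack a Day 1 to Day 43 window and a size. It matters mainly for oral corticosteroids.

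The effect on Day 43 scores cannot be estimated. It would need the share of participants whose dose changed before Day 43 and the score change that resulted, and the documents give neither. Someone might assume that 5% to 15% of participants gain 1 to 2 MG-ADL points, which gives 0.05 × 1 = 0.05 to 0.15 × 2 = 0.30 points on the mean. That range rests on nothing in the plan. It also ignores decreases, which are equally permitted, so even the direction of a net effect is unknown.

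Nor do the documents support concluding that Day 43 improvement is due to added steroids. The finding is that the planned tables would not let a reader see how often, or by how much, doses rose over that interval. The dose paths above are assumed and show only how the rule behaves.

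**What to change.** In SAP 11.1, for the by-cycle tables:

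- take Baseline ADD from the per-cycle definition in SAP 3.3, that is, the dose before that cycle's first infusion, and remove the wording tied to the first IMP in MG0007;
- report ADD, ADD change, and the number and percentage increased and decreased, from that cycle's Day 1 to Day 43 and to the end of that cycle's Observation Period (or to the day before the next cycle's first infusion, if that comes sooner).

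Keep the change from before the first MG0007 dose to the last visit as one separate entire-study table.

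Optionally, beside the all-participant results in SAP 9.1 to 9.3 and 9.5, show the Day 43 change in MG-ADL, QMG and MG-C and the MG-ADL responder rate for participants with no oral corticosteroid or AChE-inhibitor increase between Day 1 and Day 43. Label this as supportive description only. The subset is selected after baseline, possibly in relation to response, so it cannot show whether dose increases contributed to improvement.

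The cost is revised SAP wording and a few more descriptive rows, from doses, frequencies and dates already on the Concomitant Medications CRF. No change to permitted treatment is proposed.
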